2. STUDY OBJECTIVES

Primary objective Objectives

Primary Objective:	Outcome Measure:
effect of 5 weeks dapagliflozin 10mg on LDL cholesterol in patients with DM2	Change in LDL synthesis

Secondary Objective:	Outcome Measure :
Effect of 5 weeks dapagliflozin 10mg on and Triglyceride cholesterol fluxes	Change in VLDL secretion and clearance (as determined by ² H ₃ Leucine enrichment) and relation to plasma CETP, PLTP and HDL subfractions Change in De novo lipogenesis (as determined by ² H ₂ O deuterated 'heavy' water) oral 1,2,3,4- ¹³ C ₁₆ – palmitate to measure FFA remnant uptake.
Effect of 5 weeks dapagliflozin 10mg on insulin sensitivity and energy expenditure	Change in hepatic and peripheral insulin sensitivity (2 step Hyperinsulinemic normoglycemic clamp with ² H ₂ enriched glucose:) and energy expenditure including carbohydrate oxidation and fatty acid oxidation rates in breathing air
Effect of 5 weeks dapagliflozin 10mg on liver fat content (MRI liver)	Change in liverfat MRI spectrum

2.1 Safety objectives

Safety Objective: not applicable	Outcome Measure :
----------------------------------	-------------------

n/a	n/a

2.2 Exploratory objectives

Exploratory Objective:	Outcome Measure :
n/a	n/a

3. SUBJECT SELECTION, ENROLMENT, RANDOMISATION, RESTRICTIONS, DISCONTINUATION AND WITHDRAWAL

<>>

3.1 Inclusion criteria

Male or postmenopausal female patients ;

Type 2 diabetes mellitus (HbA1C \geq 6.5% - <8.5%)

At least 12 weeks a stable dose of metformin treatment > 1500mg FPG<132 mmol/l

LDL cholesterol >2.5 mmol/l,

Willing to switch used statin to crestor 10mg once daily for 9 weeks

3.2 Exclusion criteria

History of cardiovascular event

Smoking

Creatinin clearance < 60ml/min

Alcohol abuse (>4 units/day)

AST or ALT elevation (>2.5x upper limit)

3.3 Subject enrolment and randomization

All patients will receive dapagliflozin 10mg once daily.

3.4 Procedures for handling incorrectly enrolled or randomized subjects

Patients will be replaced by new patients until all 12 DM2 patients have completed the trial

3.5 Methods for assigning treatment groups

n/a

3.6 Methods for ensuring blinding

n/a

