Clinical Study Protocol

Drug Substance Dapagliflozin

Study Code DICE study

Edition Number Version 5

Date 27-06-2015

Dapagliflozin on cholesterol metabolism in DM2: dissecting its effect on dyslipidemia by using stable isotope based cholesterol and glucose fluxes; a pilot study

Sponsor:

The following Amendment(s) and Administrative Changes have been made to this protocol since the date of preparation:

Amendment No.	Date of Amendment	Local Amendment No:	Date of Local Amendment
_____	_____	_____	_____
_____	_____	_____	_____

Administrative Change No.	Date of Administrative Change	Local Administrative Change No.	Date of Local Administrative Change
_____	_____	_____	_____
_____	_____	_____	_____
_____	_____	_____	_____

PROTOCOL SYNOPSIS

Dapagliflozin on cholesterol metabolism in DM2: dissecting its effect on dyslipidemia (DICE study)

Principal Investigator

Prof dr [name], internist-endocrinologist AMC-VUMC, Amsterdam, the Netherlands

Study site(s) and number of subjects planned

AMC-VUMC Diabetes Center, 12 DM2 subjects to be included

Study period	Phase of development	
Estimated date of first subject enrolled	Q4 2015	Phase III/IV
Estimated date of last subject enrolled	Q4 2017	Phase III/IV
Dataanalyses and modelling	Q1 2018	

Study design

Single arm intervention trial

Objectives

Primary Objective:	Outcome Measure:
effect of 5 weeks dapagliflozin 10mg on LDL cholesterol in patients with DM2	Change in LDL synthesis

Secondary Objective:	Outcome Measure :

Effect of 5 weeks dapagliflozin 10mg on and Triglyceride cholesterol fluxes
 
Effect of 5 weeks dapagliflozin 10mg on insulin sensitivity and energy expenditure
 
Effect of 5 weeks dapagliflozin 10mg on liver fat content (MRI liver)
	
Change in VLDL secretion and clearance (as determined by $^2\text{H}_3$ Leucine enrichment) and relation to plasma CETP, PLTP and HDL subfractions
 
Change in De novo lipogenesis (as determined by $^2\text{H}_2\text{O}$ deuterated 'heavy' water)
 
oral $1,2,3,4-^{13}\text{C}_{16}$ – palmitate to measure FFA remnant uptake.
 
Change in hepatic and peripheral insulin sensitivity (2 step Hyperinsulinemic normoglycemic clamp with $^2\text{H}_2$ enriched glucose:) and energy expenditure including carbohydrate oxidation and fatty acid oxidation rates in breathing air
 
Change in liverfat MRI spectrum

---	--

Target subject population

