During the test only deuterated water will be served ad libitum and the subjects will remain physically inactive. After the last blood sample at T=12h patients will be offered a meal. Time series data from enrichments of plasma leucine, leucine in apoB100 from VLDL and LDL and glycerol in VLDL and LDL are used as input to the kinetic model together with pool size measurements to simultaneously determine the kinetics of VLDL-TG and apo-B100 and LDL apoB and cholesterol. (23,24).

[figure not shown]

Figure 2: study design VLDL-HDL kinetics and visit 2 and 5.

Study day 2:

Assessment of glucose metabolism and lipolysis during a 2-step hyperinsulinemic euglycemic clamp

The clamp will be performed after an overnight fast. A catheter will be inserted into an antecubital vein for infusion of the stable isotope tracers (19). Another catheter will be inserted retrogradely into a contra lateral hand vein and kept in a thermo-regulated (60°C) plexiglas box for sampling of arterialized venous blood. Saline will be infused as NaCl 0.9% at a rate of 50 mL/h to keep the catheter patent. [6,6-2H2] glucose will be used as a glucose tracer (>99% enriched; Cambridge Isotopes, Andover, USA) to study total glucose production and insulin sensitivity. [1,1,2,3,3-2H5]-glycerol (>99% enriched; Cambridge Isotopes, Andover, USA) will be used to study glycerol turnover (as a measure of total triglyceride hydrolysis/lipolysis).

At $T = -2$, blood samples will be drawn for determination of the background enrichments and primed continuous infusions will be started: [6,6-2H2] glucose (prime = 100 minutes of continuous infusion; continuous, $0.11 \mu\text{mol}/\text{kg}\cdot\text{min}$); [1,1,2,3,3-2H5]- glycerol (prime, 1.6 $\mu\text{mol}/\text{kg}$; continuous, $0.11 \mu\text{mol}/\text{kg}\cdot\text{min}$) and continued until the end of the study. At $T=0$, blood samples will be drawn for the determination of enrichments of glucose and glycerol 3 times with a 5 min interval. In addition, blood samples will be drawn for measurements of glucoregulatory hormones, free fatty acids (FFA), inflammatory markers and adipokines.

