IHTG will be quantified by ¹H-MRS on study day 2 before the clamp procedure. ¹H- MRS spectra will be acquired using a 1.0T Tesla open MRI (25). During the measurements, participants remain in the supine position within the MRI scanner. IHTG content will be obtained using single-voxel ¹H-MRS, using a body array coil as the transmitter and phased surface coils as receivers. MRS measurements will be acquired during breath-hold, using single-voxel stimulated acquisition mode. Volumes of interest in the liver will be located away from major vascular structures and bile ducts. The water and fat resonance peaks, located at 4.65 and 1.3 ppm, will be integrated using jMRUI software and relative fat content will be expressed as the ratio of the fat peak area over the cumulative water and fat peak areas. Calculated peak areas of water and fat will be corrected for T₂ relaxation (T₂water, 34 ms, T₂fat, 68 ms) and the percentage hepatic fat content will be calculated. The measurements will take approximately 30 minutes.

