5.7.2 Labelling and shipment of biological samples

Samples will be labelled according to entry number; upon shipment, they will be only be shipped by Worldcourier

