8.3 Definitions of analysis sets

Before and after dapagliflozin treatment

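### Nothing masks the kinetic modeller or the spectroscopy analyst to visit, and in this single-arm before-after trial the visit is the treatment

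*Combined protocol and SAP*

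**What the plan says.** **Design.** The synopsis describes a "Single arm intervention trial". Section 3.3 states that "All patients will receive dapagliflozin 10mg once daily", and section 8.3 gives the comparison as "Before and after dapagliflozin treatment". The flux and MRI measurements are made at week 0 and again at week 5 (section 4, Table 1).

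**Blinding.** Under the heading "3.6 Methods for ensuring blinding" the entry is n/a, as it is for treatment assignment (3.5) and unblinding (3.7).

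**Primary endpoint.** Section 2 names it as "Change in LDL synthesis". Under Study day 1 in section 1.3, the enrichment time series "are used as input to the kinetic model together with pool size measurements".

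**Liver fat.** In the part of section 1.3 on intrahepatic triglycerides, "Volumes of interest in the liver will be located away from major vascular structures and bile ducts". The water and fat peaks are then integrated in software.

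**Coding.** Section 5.7.2 says "Samples will be labelled according to entry number", and section 10.2 says that each patient receives an entry number at enrolment. Neither section mentions hiding the visit.

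**The concern.** Blinding the patient to treatment and masking the analyst to visit are separate safeguards. An open single-arm trial rules out the former but not the latter, because LDL synthesis and liver fat are both computed from stored data after the visit. As the plan stands, the person who fits a patient's two kinetic curves, or integrates the two spectra, can know which one is on dapagliflozin.

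The stated hypothesis (section 1.2) is that dapagliflozin increases LDL and VLDL secretion, so for the kinetic endpoints the expected answer is known in advance. If that knowledge shifted the derivation consistently between visits, even slightly, the estimate of the drug effect would move by the same amount. The plan has no step that would reveal this: sensitivity analysis (8.5.5) is n/a, and no rules for fitting or quality control are set out in advance.

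**Working it through.** **Step 1. Can the analyst know the treatment?**
- All patients are untreated with dapagliflozin at the week 0 measurements and treated at week 5 (3.3, Table 1). Visit therefore determines treatment.
- The only coding described is by patient (5.7.2, 10.2). It protects identity, and nothing says that it conceals the visit.
- Sections 1.3, 3.6, 5.7, 8.5 and 9.4 contain no visit masking, no random processing order and no locking of fits before the visit is known. Section 9.2.2 keeps the sponsor out of the analyses, but that does not mask the investigators' own analysts.

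So nothing in the plan prevents it.

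**Step 2. Where would a tilt go?** Let the true change be D, and let the derivation add a systematic amount b at week 5 relative to baseline. The mean of the paired differences then estimates D + b. The bias b does not shrink with sample size.

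**Step 3. How large might it be?** The plan's own planning difference (8.2) is the expected LDL-apoB synthesis on combined treatment minus that on rosuvastatin: 1.8 − 1.5 = 0.3 g/day. The documents give no figure for b, so a range is assumed as a percentage of 1.5 g/day.

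| Assumed tilt | b = tilt × 1.5 (g/day) | b / 0.3 |
|---|---|---|
| 2.5% | 0.0375 | 12.5% |
| 5% | 0.075 | 25% |
| 10% | 0.15 | 50% |

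**Step 4. Effect on false positives (illustration).** Assume no true effect, 12 patients, and an SD of the within-patient change of 0.4 g/day. Section 8.2 gives an SD of 0.4 without saying which SD it is. A paired t-test stands in for the planned signed-rank test. Its noncentrality is b/0.4 × √12, on 11 degrees of freedom, and the nominal level is 5%.

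| b (g/day) | Noncentrality | One-sided rejection rate | Two-sided rejection rate (both tails) |
|---|---|---|---|
| 0.0375 | 0.325 | 9.0% | 6.0% |
| 0.075 | 0.650 | 15.0% | 9.1% |
| 0.15 | 1.299 | 33.5% | 22.1% |

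Both columns are shown because section 8.5 does not state whether the test is one-sided. At b = 0.075, if the SD of change were 0.3 or 0.57 instead of 0.4, the one-sided rate would be 20.3% or 11.2%.

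**Sample size, for context.** From the stated inputs, ((1.645 + 1.036) × 0.4/0.3)² = 12.8, so 13 evaluable patients against the stated 11. At 80% power the same formula gives 10.99. The present point does not rest on this, and masking changes neither N, alpha nor power.

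**The case against.** The best defence is that section 3.6 is not wrong. Beside 3.5 and 3.7, n/a is a correct answer about treatment blinding when everyone gets the same open drug. The derivation is also more constrained than a critic might assume. Section 1.3 lists every sampling time, fixes apoB mass sampling at 0, 4, 8 and 12 hours, and cites published work for the kinetic model. For the spectra it gives peak positions (4.65 and 1.3 ppm), T2 corrections (34 and 68 ms) and a defined ratio. This is a 12-patient pilot, and its main weakness, the lack of a concurrent control, would remain after masking.

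Much of this stands, and it rules out several stronger readings:

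- **That the plan admits the fits need judgement.** It does not. Point weighting, dropped points and manual voxel placement are things a reader may suppose from the type of method. They are not in the text.
- **That the bias runs in the direction of a planned one-sided test.** One-sidedness appears only in the sample-size text (1.2 and 8.2). Section 8.5 states no direction, and the hypothesis gives none for liver fat.
- **That a control arm would have cancelled analyst expectation.** It would not if the analyst knew the arm. A control addresses time effects and assay drift.
- **That any bias has been shown, or its size established.** The 2.5% to 10% range is assumed.

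What the defence does not answer is the silence itself. Fixed sampling times and peak positions limit discretion but do not mask anyone, and no section says that fitting or integration is done without knowledge of the visit.

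**Conclusion.** The point holds as a gap in the plan, not as an error or contradiction. The n/a in section 3.6 is accurate for treatment, but masking of endpoint derivation is possible here and is not provided. Because visit equals treatment, the modeller and the spectroscopy analyst can know which data are on dapagliflozin, and any systematic pre/post difference in derivation passes undiluted into the estimated effect.

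Under the assumed tilt of 2.5% to 10%, the shift is 0.04 to 0.15 g/day, about 13% to 50% of the planned 0.3 g/day. The false-positive rates additionally assume an SD of change of 0.4 g/day and a paired t-test. The actual size is unknown, because the documents do not say how much discretion the steps leave. Exposure differs by endpoint: directly measured outputs such as indirect calorimetry leave less room than model-derived rates. The change is worth making because it protects the primary endpoint at little cost.

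**What to change.** Replace n/a in section 3.6 with text along these lines:

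> Treatment is open; endpoint derivation is masked to visit. Existing staff not involved in modelling relabel each patient's two visits with random codes for enrichments, pool sizes and acquired spectra. The modeller and the spectroscopy analyst complete and lock all fits and peak integrations under those codes before the visit key is released.

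Add a cross-reference in 5.7.2 so that the samples and data files passed on for analysis carry the code and not the visit.

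Two further steps are worth adding, described as control of assay drift and repeatability and not as masking: assay both visits of a patient in the same run, and match the voxel position at the second scan to the baseline scan. The voxel is placed at acquisition, when the visit is known, so relabelling cannot mask that step.

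**Cost.** A coding list, someone to hold the key, and an agreed order of runs; no extra patient procedure, and no change to N, alpha or power. Results wait for each patient's second visit, which fits the 3 to 6 months that section 9.3 already sets aside for analysis and modelling. Clamp glucose data may reveal the visit, so masking will be less secure there. Time effects and regression to the mean remain, and the report should say so.

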3.7 Methods for unblinding

n/a

3.8 Restrictions

None

3.9 Discontinuation of investigational product

3.9.1 Procedures for discontinuation of a subject from investigational product

Patients will be replaced by new patients until all 12 DM2 patients have completed the trial. Dropout patients will be followed up until 3 months after cessation of the trial.

3.10 Criteria for withdrawal

none

3.10.1 Screen failures

When patients do not match inclusion criteria, they will not be enrolled in the trial.

3.10.2 Withdrawal of the informed consent

Patients will be replaced by new patients until all 12 DM2 patients have completed the trial. Dropout patients will be followed up until 3 months after cessation of the trial.

3.11 Discontinuation of the study

Dropout patients will be followed up until 3 months after cessation of the trial.

4. STUDY PLAN AND TIMING OF PROCEDURES

Clinical Study Protocol
 Drug Substance Dapagliflozin
 Study Code DICE study
 Edition Version 5
 Date 28-02-2015

Table 1 Study Plan DICE study detailing the procedures

Visit	1	2	3	4	5	6	For details see Protocol Section
Week	0	0	2.5	5	5		
Day	-						
Written informed consent (including tissue samples)	X						
Demographics	X						
Physical examination, height and weight	X			X		X	
Medical/surgical history/ECG	X						
Inclusion/exclusion criteria	X						
Fluxes and MRI		X	X		X	X	
Vital signs	X	X	X	X	X	X	
Start study treatment			X				
Treatment dispensed/returned	X	X				X	
Concomitant medication	X	X	X	X	X	X	

Visit	1	2	3	4	5	6	For details see Protocol Section
Visit window	Screening and start rosuvastatin						
Days -28 to 0 for Visit 1							
7 ±1 day for Visit 2& 3							
7 ±1 day for Visits 4							
7 ±1 day for Visit 5&6							
Week	0	0	2.5	5	5		
Day	-						
Adverse event review (AEs and SAEs)		X	X	X	X	X	
Blood samples for haematology and clinical chemistry	X	X	X	X	X	X	
24h Urinalysis		X	X		X	X	

4.1 Enrolment/screening period

Q3 2015

4.2 Treatment period

5 weeks

4.3 Follow-up period

none

5. STUDY ASSESSMENTS

5.1 Efficacy assessments

Change in lipolysis using plasma VLDL-TG clearance (as determined by $^2\text{H}_5$ glycerol enrichment)

Change in VLDL-TG secretion and clearance (as determined by $^2\text{H}_3$ Leucine enrichment) in relation to plasma CETP, PLTP and HDL subfractions

Change in cholesterol mobility (13C cholesterol enrichment in LDL and HDL)

Change in De novo lipogenesis (as determined by $^2\text{H}_2\text{O}$ deuterated 'heavy' water)

oral 1,2,3,4- $^{13}\text{C}_{16}$ – palmitate to measure FFA remnant uptake.

5.2 Safety assessments

5.2.1 Laboratory safety assessments

Haematology/Haemostasis (whole blood)	Clinical Chemistry (serum or plasma)
B-Haemoglobin (Hb)	S/P-Creatinine
B-Leukocyte count	S/P-Bilirubin, total
B-Leukocyte differential count (absolute count)	S/P-Alkaline phosphatise (ALP)
B-Platelet count	S/P-Aspartate transaminase (AST)
	S/P-Alanine transaminase (ALT)
Urinalysis (dipstick)	S/P-Albumin
U-Hb/Erythrocytes/Blood	S/P-Potassium
U-Protein/Albumin	S/P-Calcium, total
U-Glucose	S/P-Sodium

>>

5.2.2 Physical examination

Regular

5.2.3 ECG

5.2.3.1 Resting 12-lead ECG

Done on screeningsvisit

5.2.4 Vital signs

Will be taken according to AMC Vascular Medicine SOP

5.2.4.1 Pulse and blood pressure

Will be taken according to AMC Vascular Medicine SOP

5.2.4.2 Body temperature

Will not be taken routinely

5.2.5 Other safety assessments

n/a

5.3 Other assessments

5.3.1 Patient reported outcomes

Not used

5.4 Pharmacokinetics

5.4.1 Collection of samples

n/a

5.4.2 Determination of drug concentration

n/a

5.4.3 Storage and destruction of pharmacokinetic samples

n/a

5.5 Pharmacodynamics

5.5.1 Collection of samples

n/a

5.5.2 Storage, re-use and destruction of pharmacodynamic samples

n/a

5.6 Pharmacogenetics

5.6.1 Collection of pharmacogenetic samples

n/a

5.6.2 Storage, re-use and destruction of pharmacogenetic samples

n/a

5.7 Biomarker analysis

5.7.1 Storage, re-use and destruction of biological samples

Samples will be stored at -80C at AMC and used for analyses. Upon 5 years after completion of the study, samples will be destroyed.

5.7.2 Labelling and shipment of biological samples

Samples will be labelled according to entry number; upon shipment, they will be only be shipped by Worldcourier

5.7.3 Chain of custody of biological samples

Samples will be owned by AMC hospital

5.7.4 Withdrawal of Informed Consent for donated biological samples

Samples will be destroyed upon retraction of informed consent.

6. SAFETY REPORTING AND MEDICAL MANAGEMENT

6.1 Definition of adverse events

Adverse events are defined as any undesirable experience occurring to a subject during a clinical trial, whether or not considered related to the investigational drug or deterioration of a pre-existing medical condition. All adverse events reported spontaneously by the subject or observed by the investigator or his staff will be recorded.

6.2 Recording of adverse events

Will be recorded in CRF

6.2.1 Time period for collection of adverse events

During 9 weeks of being in the study

6.2.2 Follow-up of unresolved adverse events

Patients will be followup until 3 months after end of trial visit

6.2.3 Variables

Adverse events are defined as any undesirable experience occurring to a subject during a clinical trial, whether or not considered related to the investigational drug. All adverse events reported spontaneously by the subject or observed by the investigator or his staff will be recorded. The following variables should be collected for each AE;

- *AE (verbatim)*
- *The date and time when the AE started and stopped*
- *Whether the AE is serious or not*
- *Investigator causality rating against the Investigational Product (yes or no)*
- *Action taken with regard to investigational product*
- *AE caused subject's withdrawal from study (yes or no)*

- *Outcome.*
- *In addition, the following variables should be collected for SAEs:*
- *Date AE met criteria for serious AE*
- *Date Investigator became aware of serious AE*
- *AE is serious due to...*
- *Date of hospitalisation*
- *Date of discharge*
- *Probable cause of death*
- *Date of death*
- *Autopsy performed*
- *Causality assessment in relation to Study procedure(s)*
- *Description of AE*
- *Causality to assessment in relation to study procedure(s)*
- *Causality assessment in relation to other medication*
- *(Causality assessment in relation to additional study drug)*
-

6.2.4 Causality assessment

Causality will be assessed by study physician and Principle Investigator.

6.2.6 Disease progression

Not applicable in such a short timeframe

6.3 Reporting of serious adverse events

A serious adverse event is an important medical event that may jeopardize the subject or may require medical intervention to prevent one of the outcomes listed above any untoward medical occurrence, effect or deterioration of a pre-existing medical condition that at any dose:

- results in death;
- is life-threatening (at the time of the event);
- requires hospitalization or prolongation of existing inpatients' hospitalization;
- results in persistent or significant disability or incapacity;
- is a congenital anomaly or birth defect;
- The Principal Investigator is responsible for ensuring that all staff involved in the study is familiar with the content of this section. In accordance to section 10, subsection 1, of the WMO, the investigator will inform immediately the subjects, the reviewing accredited MEC and concurrently AstraZeneca if anything occurs, on the basis of which it appears that the disadvantages of participation may be significantly greater than was foreseen in the research proposal. The study will be suspended pending further review by the accredited MEC/IRB, except insofar as suspension would jeopardise the subjects' health. The investigator will take care that all subjects are kept informed.

The investigator will report the SAE's through the web portal ToetsingOnline to the accredited METC that approved the protocol, within 15 days after the investigator has first knowledge of the serious adverse reaction and concurrently to AZ.

SAE's that result in death or are life threatening should be reported expedited. The expedited reporting will occur not later than 7 days after the investigator has first knowledge of the adverse reaction. This is for a preliminary report with another 8 days for completion of the report. Also, a concurrently SAE report and accompanying cover page will be send by e-mail ([contact]) to AstraZeneca TCS Data Entry Site.

On behalf of the sponsor, the PI will submit once a year an Annual Safety Report to the accredited MEC and competent authority.

